5.5 Derived Variables

All questionnaire scores will be derived by Biostatistics in the ADaM datasets using the formulas defined below, even if calculated scores are present in the EDC database. All pre-calculated scores will be ignored for analysis.

	STATISTICAL ANALYSIS PLAN, Version 3.0
Protocol Number: ARQ-151-311	Sponsor: Arcutis Biotherapeutics, Inc.

- With the following exception, vIGA-AD Success = vIGA-AD of ‘Clear’ (0) or ‘Almost Clear’ (1) plus at least a 2-grade improvement from Baseline. The exception is that for subjects who discontinued early from study due to an AE or lack of efficacy, the subject will be considered as not having a vIGA-AD success (for MI and non-responder imputation analyses) or missing (for observed case analyses) for all pre-specified analysis visits (refer to Section 5.4) for which the subject’s last dose day falls within analysis visit window or is prior to the start of the analysis visit window.
- Average weekly WI-NRS = Average weekly WI-NRS pruritus score will be calculated as the sum of the daily WI-NRS scores reported during a specific week (in a 7-day period; refer to Section 5.4) of the study divided by the number of days with non-missing scores for that week. A minimum of 4 days of observations are needed to calculate an average weekly WI-NRS pruritus score. Otherwise, the corresponding average weekly WI-NRS pruritus score will be considered missing.
- With the following exception, a WI-NRS 4-point reduction = achievement of a 4- point reduction in average weekly WI-NRS pruritus score compared to average weekly WI-NRS baseline, calculated only for the subjects ≥ 12 years old with average weekly WI-NRS score of ≥ 4 at baseline. The exception is that for subjects who discontinued early from study due to an AE or lack of efficacy, the subject will be considered as not having a WI-NRS 4- point reduction (for MI and non-responder imputation analyses) or missing (for observed case analyses) for all pre-specified analysis visits (refer to Section 5.4) for which the subject’s last dose day falls within the analysis visit window or is prior to the start of the analysis visit window.
- EASI total score = $0.1 (E_h + I_h + E_{Xh} + L_h) A_h + 0.2 (E_u + I_u + E_{Xu} + L_u) A_u + 0.3 (E_t + I_t + E_{Xt} + L_t) A_t + 0.4 (E_l + I_l + E_{Xl} + L_l) A_l$
for subjects ‘ ≥ 8 years old’
and
 $0.2 (E_h + I_h + E_{Xh} + L_h) A_h + 0.2 (E_u + I_u + E_{Xu} + L_u) A_u + 0.3 (E_t + I_t + E_{Xt} + L_t) A_t + 0.3 (E_l + I_l + E_{Xl} + L_l) A_l$
for subjects < 8 years old

where E, I, Ex, L, and A denote erythema, induration, excoriation, lichenification, and area, respectively, and h, u, t, and l denote head, upper extremities, trunk, and lower extremities, respectively. Scalp, palms, and soles may be treated with investigational product in this study but will be excluded from the EASI assessment. If a subject turns 8 years old during the study, the formula used at Screening will continue to be used through the study duration of the subject’s participation in the study.

	STATISTICAL ANALYSIS PLAN, Version 3.0
Protocol Number: ARQ-151-311	Sponsor: Arcutis Biotherapeutics, Inc.

- With the following exception, EASI-50, EASI-75, EASI-90, and EASI-100 = Achievement of at least a 50%, 75%, 90%, or 100% reduction from baseline in EASI total score, respectively. The exception is that for subjects who discontinued early from study due to an AE or lack of efficacy, the subject will be considered as not having reached EASI-50, EASI-75, EASI-90 and EASI-100 (for MI and non-responder imputation analyses) or missing (for observed case analyses) for all pre-specified analysis visits (refer to Section 5.4) for which the subject's last dose day falls within the analysis visit window or is prior to the start of the analysis visit window.
- DLQI Score = sum of the 10 questions (individual questions scored as Very much=3, A lot=2, A little=1, Not at all=0, Not relevant=0, Question 7: Yes=3, if No, then follow the same score as A lot, A little, Not at all), ranging from 0 to 30. If 1 item is missing, it is scored as 0 for that item. If 2 or more items are missing, the score should not be calculated.
- CDLQI Score = sum of the 10 questions (individual questions scored as Very much=3, Quite a lot=2, Only a little=1, Not at all=0; Question 7: if the last week was school time, the question was scored as Very much=3, Quite a lot=2, Only a little=1, Not at all=0, with Prevented school recoded to 3, and if the last week was holiday time, the standard responses apply), ranging from 0 to 30. If 1 item is missing, that item is scored as 0. If 2 or more items are missing, the score should not be calculated.
- DFI Score = sum of the 10 questions (individual questions scored as Very much=3, A lot=2, A little=1; Not at all=0), ranging from 0 to 30. If 1 item is missing, it is scored as 0 for that item. If 2 or more items are missing, the score should not be calculated.
- PHQ-8 = sum of the 8 questions (individual questions scored as Not at all=0, Several days=1, More than half the days=2, and Nearly every day=3), ranging from 0 to 24. If more than 1 item is missing the score should not be calculated. If 1 item is missing the score is calculated as (sum of answered items*8)/number of answered items (=7).
- Modified PHQ-A = sum of the 8 questions (individual questions scored as Not at all=0, Several days=1, More than half the days=2, and Nearly every day=3), ranging from 0 to 24. If more than 1 item is missing the score should not be calculated. If 1 item is missing, the score is calculated as (sum of answered items*8)/number of answered items (=7).
- CDI-2 total score is a sum of the 17 questions based on the scoring grid (individual questions scored as much or most of the time=0, often=1, some of the time=2, Not at all=3 for questions Q2, Q7, Q13, Q14, and Q16; individual questions scored as much or most of the time=3, often=2, some of the time=1, Not at all=0 for all other questions), ranging from

	STATISTICAL ANALYSIS PLAN, Version 3.0
Protocol Number: ARQ-151-311	Sponsor: Arcutis Biotherapeutics, Inc.

0 to 51. All CDI-2 raw scores can be prorated using the following formula, rounding to the nearest whole number:

- Prorated score = (Obtained raw score for scale) * (Total # of items on scale/subscale) / Total # items on scale/subscale with responses
- CDI-2 emotional problem scale is a sum of 9 questions (Q1, Q3-6, Q8, Q10-12). If more than 1 item is missing the score should not be calculated. If 1 item is missing the score is calculated as (sum of answered items*9)/number of answered items (=8).
- CDI-2 functional problem scale is a sum of 8 questions (Q2, Q7, Q9, Q13-17). If more than 1 item is missing the score should not be calculated. If 1 item is missing the score is calculated as (sum of answered items*8)/number of answered items (=7).
- CDI-2 total score is a sum of 17 questions. If more than 2 items are missing the score should not be calculated. If 1 item is missing the score is calculated as (sum of answered items*17)/number of answered items (=16). If 2 items are missing the score is calculated as (sum of answered items*17)/number of answered items (=15).
- POEM = sum of the 7 questions (individual questions scored as No days = 0, 1 to 2 days = 1, 3 to 4 days = 2, 5 to 6 days = 3, Every day = 4), ranging from 0 to 28. If 1 question is left unanswered this is scored 0 and the scores are summarized and expressed as usual out of a maximum of 28. If 2 or more questions are left unanswered the questionnaire is not scored.
- SCORAD = [Overall BSA affected by AD / 5] + [Intensity score*7/2] + subjective symptoms score (pruritus + sleep loss); SCORAD score will be set to missing if information for any of the three measures is missing.

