1 INTRODUCTION

This Statistical Analysis Plan (SAP) describes the planned analysis and reporting for Arcutis Biotherapeutics, Inc. clinical protocol ARQ-151-311. The analyses described in the SAP are based upon the protocol Amendment 4 dated 28 September 2022. In case of changes (note that any such changes are described in section 3.5 below) between the protocol and the SAP, the SAP will be used to guide the statistical analysis. Any deviations from the SAP will be described and justified in the final Clinical Study Report (CSR), as appropriate.

On [REDACTED] FDA provided the following advice in preliminary feedback prior to a pre-NDA meeting held with Arcutis for a similar program on [REDACTED]

For the primary estimand, you [Arcutis] proposed a treatment policy strategy to handle all intercurrent events, including treatment discontinuation due to adverse event or lack of efficacy. For intercurrent events of treatment discontinuation due to adverse events or lack of efficacy, we [FDA] recommend a composite strategy policy where subjects will be defined as non-responders, as we consider this to be the appropriate approach for handling such events. Your proposal to handle intercurrent events of treatment discontinuation using the treatment policy strategy can be used as part of a supportive estimand.

The purpose of this version of the SAP is to document the change to the primary estimand and related multiple imputation strategies as requested by the FDA for a similar program.

This SAP has been developed prior to database lock, unblinding, and associated analyses. All final analyses will be performed after approval of the SAP, the clinical trial data are entered into the database, any discrepancies in the data are resolved, determination of the inclusion/exclusion of each subject from each analysis population, the database is locked, and the unblinding request form is signed.

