6.2.1 Multiple Imputation

All subjects, regardless of completion status, will have available data assigned to the pre-specified analysis visit using the analysis windows defined in Section [5.4](#), including the last available data

	STATISTICAL ANALYSIS PLAN, Version 3.0
Protocol Number: ARQ-151-311	Sponsor: Arcutis Biotherapeutics, Inc.

of subjects who prematurely withdraws from the study. To comply with the definition of the primary estimand (Section 12.1.1), for subjects who discontinue due to lack of efficacy or adverse event, efficacy data assigned to a pre-specified analysis visit will be removed from the source data used for the multiple imputation process if subject's last dose day falls within the analysis visit window or is prior to the start of the analysis visit window used to assign data to a pre-specified analysis visit. Similarly, WI-NRS weekly averages will be removed from the source data used for multiple imputation if subject's last dose day falls within the analysis visit window or is prior to the start of the interval used to compute the weekly average as defined in Section 5.4. This procedure will ensure that the data collected on or after intercurrent events are not used in the imputation process.

For the primary efficacy endpoint of vIGA-AD success at Week 4 and the secondary endpoint of vIGA-AD success at Week 4 among subjects with a 'Moderate' randomized vIGA-AD score, the primary analysis will impute missing values using a Predictive Mean Matching (PMM) sequential-regression multiple imputation model for the ITT population. This is a three-step process.

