12 EFFICACY ANALYSIS

12.1 Primary Efficacy Endpoint Analysis

12.1.1 Primary Efficacy Endpoint and Estimand

The vIGA-AD is a static evaluation of qualitative overall AD severity. This global assessment scale is an ordinal scale with five severity grades (reported only in integers of 0 to 4). Each grade is defined by a distinct and clinically relevant morphologic description that minimizes inter-observer variability. vIGA-AD is evaluated for the entire body except the scalp, palms, and soles.

The primary efficacy endpoint is vIGA-AD success, defined as an vIGA-AD score of ‘clear’ (0) or ‘almost clear’ (1) plus at least a 2-grade improvement from Baseline at Week 4.

The primary estimand is described by the following attributes:

Population: Patients with Atopic Dermatitis

Endpoint: vIGA-AD success at Week 4

Intercurrent events: In the course of the 4-week randomized treatment period, subjects may be exposed to possible known or unknown intercurrent events that could possibly impact the estimates of the estimand, such as treatment discontinuation due to a specific adverse effect or perhaps a lack of effect. A composite strategy will be implemented that handles subjects who discontinue due to lack of efficacy or adverse event as missing not at random differently than all other subjects. That is, subjects who discontinue due to lack of efficacy or adverse event will be treated as non-responders for all pre-specified analysis visits (refer to Section 5.4) for which the subject’s last dose day falls within the analysis window or is prior to the start of the analysis window (refer to

	STATISTICAL ANALYSIS PLAN, Version 3.0
Protocol Number: ARQ-151-311	Sponsor: Arcutis Biotherapeutics, Inc.

Section 5.5) while the “Treatment Policy Strategy” will be adopted for handling intercurrent events in this study other than discontinuation due to lack of efficacy or adverse event.

Population-level summary: ratio of the odds of achieving vIGA-AD success after 4 weeks of using roflumilast cream 0.15%, relative to the odds of success after 4 weeks using a matching vehicle cream in the ITT population.

The supportive population-level summary: the proportion difference between Roflumilast cream 0.15% and vehicle groups will be provided for the patients who achieve vIGA-AD success at week 4 in the ITT population.

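### The composite non-responder rule in SAP 5.5 is triggered by leaving the study, not by stopping treatment, and it has no entry for vIGA-AD clear/almost clear

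*SAP*

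**What the plan says.** SAP 1 reports regulatory advice from a similar program: "For intercurrent events of treatment discontinuation due to adverse events or lack of efficacy, we [FDA] recommend a composite strategy policy", with such subjects defined as non-responders. On the sponsor's alternative the advice was: "Your proposal to handle intercurrent events of treatment discontinuation using the treatment policy strategy can be used as part of a supportive estimand". The section says that v3.0 was written to document this change.

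SAP 12.1.1 illustrates the intercurrent events with "such as treatment discontinuation due to a specific adverse effect or perhaps a lack of effect". It then states the rule without saying what is discontinued: "subjects who discontinue due to lack of efficacy or adverse event will be treated as non-responders for all pre-specified analysis visits". Treatment policy "will be adopted for handling intercurrent events in this study other than discontinuation due to lack of efficacy or adverse event". It refers to SAP 5.5.

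SAP 6.2.1 also leaves the object open: "for subjects who discontinue due to lack of efficacy or adverse event, efficacy data assigned to a pre-specified analysis visit will be removed" from the imputation source when the last dose day falls in or before the visit window. It adds: "This procedure will ensure that the data collected on or after intercurrent events are not used in the imputation process". Step 3 computes the response variables from the completed datasets by the definitions in SAP 5.5.

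SAP 5.5 is the only place that names the trigger. For vIGA-AD Success it covers "subjects who discontinued early from study due to an AE or lack of efficacy, the subject will be considered as not having" a success. The WI-NRS 4-point reduction and EASI-50/75/90/100 have the same study-level trigger. There is no entry for vIGA-AD clear/almost clear, although SAP 12.2 says the secondary endpoints are derived in 5.5.

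SAP 6.2.3 refers to Step 2 of 6.2.1 for keeping these subjects as non-responders.

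**The concern.** Stopping study treatment and leaving the study are different events, and SAP 13.1 tabulates AEs leading to each separately. The advice concerns the first; the derivation acts on the second. A programmer following SAP 5.5 would leave a treatment-stopper who remains in the study without a reset, in the primary analysis of a plan revised to prevent exactly that.

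The missing clear/almost clear entry affects tested endpoints. At Week 4 this endpoint is second in the fixed Family 2 sequence, so it gates the four endpoints after it. Half of Family 2 lacks a stated rule for subjects who drop out for an AE or lack of efficacy.

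**Working it through.** **1. Who is reset.** Take a subject who stops treatment for an AE or lack of efficacy, stays in the study and has a Week 4 score.

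| Reading of 6.2.1 | Trigger in 5.5 | Result |
|---|---|---|
| Study discontinuation | Study, as written | Observed score counts: treatment policy |
| Treatment discontinuation | Study, as written | Score removed and imputed, no reset |
| Treatment discontinuation | Treatment, as advised | Non-responder |

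Under either reading of 6.2.1, SAP 5.5 as written gives no reset. Its last-dose-day clause decides which visits are affected, not which subjects.

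**2. Clear/almost clear.** For a dropout, 6.2.1 removes the affected scores and imputes them. Step 3 sends the derivation to 5.5, which has no entry, so no written step sets the subject to non-response. SAP 6.2.2 classifies this endpoint from the visit score alone; that sentence deals with a missing baseline and adds no exception. From a baseline of 3, a score of 0 or 1 is automatically a 2-grade improvement. In Moderate subjects (about 490 of 650, SAP 5.1) Success and clear/almost clear are therefore the same event, scored under different rules.

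**3. Cross-reference.** Step 2 of 6.2.1 contains the predictive mean matching model and no non-responder rule.

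**4. Size, primary endpoint.** Inputs from the SAP: N = 650 at 2:1, so 433/217; planning rates 37% and 22% (5.1). Assumption: 1–3% per arm stop treatment for these reasons, stay, and respond at the planning rates. The standard error (SE) is unstratified and ignores imputation variance.

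- SE = √(0.37×0.63/433 + 0.22×0.78/217) = 3.65 points; planned Z = 15/3.65 = 4.11.
- Shift in the difference (literal minus composite) = 37% × active share − 22% × vehicle share:
  - 1%/1%: 0.37 − 0.22 = +0.15 points
  - 3%/3%: 1.11 − 0.66 = +0.45
  - 3%/1%: 1.11 − 0.22 = +0.89 (+0.244 SE)
  - 1%/3%: 0.37 − 0.66 = −0.29 (−0.080 SE)
- The decision at 0.05 can change only for an observed z between 1.960 − 0.080 (p = 0.060) and 1.960 + 0.244 (p = 0.028).
- At half these response rates: −0.04 to +0.12 SE, p about 0.037 to 0.055.
- Stress test with one response rate of 37% in both arms: equal shares leave the difference unchanged. With 5%/2% or 2%/5% it moves by 0.37 × 3 = 1.11 points, or 1.11/3.65 = 0.30 SE.

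**5. Size, clear/almost clear at Week 4.** Assumptions: 1–3% dropouts per arm, imputed at 45% and 30% (neither set is in the documents for this endpoint).

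- SE = √(0.45×0.55/433 + 0.30×0.70/217) = 3.92 points.
- 3%/1%: 1.35 − 0.30 = +1.05 points (+0.268 SE). 1%/3%: 0.45 − 0.90 = −0.45 points (−0.115 SE).
- At alpha 0.02 (z = 2.326) the decision can change for p about 0.009 to 0.027; at alpha 0.05, about 0.026 to 0.065.
- At half the imputed rates: −0.06 to +0.13 SE, p about 0.014 to 0.023 at alpha 0.02.

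**6. Size, Moderate stratum.** 490 at 2:1 = 327/163. The SAP 5.1 rates are 28% vehicle and 28 + 17 = 45% active.

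- Dropouts at 1–3%: 3.3–9.8 active, 1.6–4.9 vehicle.
- Failures on Success but responders on the identical event: ×45% = 1.5–4.4 active; ×28% = 0.5–1.4 vehicle.

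**The case against.** The intent can be inferred. SAP 12.1.1 names treatment discontinuation before stating the rule, the timing runs on last dose day throughout, and 6.2.3 speaks of visits on or after discontinuation of treatment. The pointer from 12.1.1 to 5.5 follows the timing clause and may be about timing only. SAP 12.2 says secondary endpoints are handled as the primary is, and the neighbouring EASI and WI-NRS entries make the missing one easy to guess. This shows what was probably meant. But Step 3 of 6.2.1 takes the derivation from 5.5, where the trigger is study-level and the entry is absent. Inferred intent does not replace a stated derivation in a primary analysis.

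Nothing in the documents shows that anyone falls in the gap. That stands. Protocol 5.9 has treatment stopped permanently for a recurrent application site reaction while the subject is followed, but that may be safety follow-up only. The protocol supplied is the original, whereas the SAP rests on Amendment 4. The mismatch inside the SAP does not depend on it.

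The sizes lean high. That also stands: the imputation model conditions on earlier vIGA-AD scores, so lack-of-efficacy dropouts would probably be imputed as responders less often than assumed. The half-rate results reflect this.

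The 6.2.3 cross-reference is clerical on its own.

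**Conclusion.** The concern holds. Followed literally, SAP 5.5 departs from the estimand SAP 1 says it adopts, and the same 0/1 score in a Moderate subject can be counted differently on two tested endpoints. On the assumed 1–3% per arm, the primary result moves by −0.08 to +0.24 SE and clear/almost clear at Week 4 by −0.11 to +0.27 SE. The sign depends on which arm has more such subjects. At the planned Z of 4.11 the primary conclusion would not change; only a result near its alpha could, in either direction. It should be fixed because the plan leaves open how these subjects are scored, not because the expected bias is large.

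**What to change.** Before unblinding:

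- Use one trigger in SAP 5.5, 6.2.1, 6.2.3 and 12.1.1: discontinued study treatment or the study due to an AE or lack of efficacy, with the reason recorded at either level. Keep the last-dose-day timing.
- Add a 5.5 entry for vIGA-AD clear/almost clear with the same exception for the multiple-imputation, non-responder and observed-case analyses. Do the same for clear; as an exploratory endpoint analysed on observed data (SAP 12.3), it needs only the observed-case part.
- Point 6.2.3 to 5.5 instead of Step 2 of 6.2.1.

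The cost is SAP wording and one derivation. Response rates may come out slightly lower. The sponsor must confirm under blind where the reason for stopping treatment is captured, because SAP 7.1 tabulates reasons only for study discontinuation. The either-level wording keeps subjects whose reason is recorded only there.

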12.1.3 Primary Endpoint Analysis

For the primary analysis, missing vIGA-AD scores will be imputed using multiple imputation as described in Section 6.2.1. These imputations will result in a minimum of 25 to a maximum of 250 complete analysis datasets, depending on the number of imputed monotone datasets that are required.

Percentages of subjects having a vIGA-AD Success (refer to Section 12.1.1) will be presented by visit and treatment group based on multiply imputed data in the ITT population along with a 95% Wilson CI. The common MH odds ratio and common MH proportion difference, adjusted for the randomization factors (i.e., randomized vIGA-AD score and pooled study site) will also be provided along with their common associated 95% CIs. Additionally, count and percentage of subjects having a vIGA-AD success, count and percentage of subjects in each category of the vIGA-AD scale, and descriptive statistics for the vIGA-AD scores, change in vIGA-AD score from

	STATISTICAL ANALYSIS PLAN, Version 3.0
Protocol Number: ARQ-151-311	Sponsor: Arcutis Biotherapeutics, Inc.

baseline and percent change in vIGA-AD score from baseline will be presented by visit and treatment group based on observed data in the ITT population.

The primary endpoint (vIGA-AD Success at Week 4) will then be analyzed using multiple imputation CMH test stratified by the randomization factors. To do so, a CMH analysis will be performed separately for each of the complete multiply imputed analysis data sets, and results will be combined into one multiple imputation inference using the methodology described in Section 6.2.1. Statistical significance will be concluded at the 5% significance level (2-sided). Should the odds ratio be not estimable for at least one multiply imputed dataset, the conclusion of the study will be based on the p-value obtained from a MH test, stratified by the randomization factors, for the common MH proportion difference at Week 4.

The following sensitivity analyses to the primary analysis of the primary endpoint will be performed:

- Multiply-imputed data (refer to Section 6.2.1) on mITT population (refer to Section 4.2) and
- Tipping Point analysis (refer to Section 6.2.3) on ITT population.
- Non-responder imputation (refer to Section 6.2.2) on ITT population.
- Observed data on ITT population (refer to Section 4.1).
- Observed data on PP population (refer to Section 4.3).

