For each categorical exploratory efficacy endpoint, count and percentages of subjects meeting the criteria for an exploratory efficacy endpoint will be presented by visit and treatment group based on observed data in the ITT population along with a 95% Wilson CI. Additionally, count and percentage of subjects meeting the criteria for vIGA-AD of Clear (0), EASI-50, EASI-90, and EASI-100 at Week 1 and Week 2 will also be presented by visit and treatment group based on observed data in the ITT population along with a 95% Wilson CI.

Continuous exploratory efficacy endpoints will be analyzed at Week 1, Week 2, and Week 4 and for daily WI-NRS assessments using an analysis of covariance (ANCOVA) with the factors of treatment, two stratification variables (pooled study site and randomized vIGA-AD score), and baseline of the variable under analysis as covariate. Statistical comparisons between the treatment groups will be obtained using contrasts. The Least Square (LS) mean and its standard error, difference in LS means between treatment group (i.e., active - vehicle), its standard error and associated 95% confidence interval, and p-value for difference from vehicle will be presented at each visit. These analyses will be performed based on observed data in the ITT population.

Categorical exploratory efficacy endpoints at Weeks 1, 2, and 4 will be analyzed using a CMH test adjusted for the two stratification variables (pooled study site and randomized vIGA-AD score). Common MH odds ratio, common MH proportion difference and their common associated 95% CI, adjusted for the randomization factors, will be provided. The p-value will be from a CMH test for the common MH odds ratio, unless the common MH odds ratio is not estimable. In such circumstances, the p-value will be from a MH test for the common MH proportion difference.

The analysis of these endpoints will be performed on the observed data with no imputation. The p-values will be nominal as no formal inferential testing will be done on exploratory efficacy endpoints.

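### Observed-case analyses drop AE and lack-of-efficacy discontinuers whom the composite estimand counts as non-responders, yet most are labelled sensitivity analyses

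*SAP*

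**What the plan says.** SAP Section 1 explains that this version adopts regulatory advice given on a similar program. For treatment discontinuation due to AE or lack of efficacy, the agency wrote that it would "recommend a composite strategy policy where subjects will be defined as non-responders". SAP 12.1.1 puts this into the primary estimand: "subjects who discontinue due to lack of efficacy or adverse event will be treated as non-responders for all pre-specified analysis visits", with a treatment policy strategy for all other intercurrent events.

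SAP 5.5 turns the strategy into derivation rules. For vIGA-AD success, at every visit whose window contains the last dose day or opens after it, "the subject will be considered as not having a vIGA-AD success (for MI and non-responder imputation analyses) or missing (for observed case analyses". The WI-NRS 4-point reduction has the same exception: failure in the multiple imputation and non-responder analyses, "or missing (for observed case analyses". So do the EASI responder levels: "not having reached EASI-50, EASI-75, EASI-90 and EASI-100 (for MI and non-responder imputation analyses) or missing (for observed case analyses".

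The observed-case analyses are used in two ways:

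- As sensitivity analyses. SAP 12.1.3 begins its list with "The following sensitivity analyses to the primary analysis of the primary endpoint will be performed" and includes "Observed data on ITT population (refer to Section 4.1" and the per-protocol (PP) counterpart. SAP 12.2 and the summary table in 12.5 do the same for Moderate ITT, Moderate PP, the WI-NRS population and the remaining secondary endpoints. The secondary ones are run only if the testing hierarchy allows.
- As the only analysis. For the exploratory endpoints, SAP 12.3 states: "The analysis of these endpoints will be performed on the observed data with no imputation". The p-values there are nominal.

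**The concern.** Under a composite strategy the discontinuation is the outcome. Once a subject stops for an AE or lack of efficacy, the responder status is known to be failure and nothing is missing. Setting it to missing only in the observed-case analyses changes the question from success among all randomized subjects to success among those who did not stop for these reasons. The SAP defines no estimand for that second quantity.

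A sensitivity analysis should keep the estimand and vary the assumptions about data that are truly missing. Here the target changes as well, so a gap between the observed-data and primary results could come partly or wholly from removing these subjects and be misread as sensitivity to missing data. For EASI-50, EASI-90 and EASI-100 no companion analysis counts these failures. The observed-data counts and percentages of vIGA-AD success by visit (SAP 12.1.3) follow the same rule.

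**Working it through.** The plan gives no figure to reproduce, because the dispute is about a derivation rule. The check sets the provisions side by side and then sizes the effect.

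**Step 1. How each planned analysis of the primary endpoint treats an AE or lack-of-efficacy discontinuer**

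| Analysis | Treatment | Source |
|---|---|---|
| Multiple imputation, ITT (primary) | failure | SAP 5.5, 12.1.1 |
| Multiple imputation, mITT | failure | SAP 5.5, 12.1.3 |
| Tipping point | failure | SAP 6.2.3 |
| Non-responder imputation | failure | SAP 5.5, 6.2.2 |
| Observed data, ITT | missing | SAP 5.5, 12.1.3 |
| Observed data, PP | missing, if still in the PP set | SAP 5.5, 4.3 |

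Only the last two rows depart from the estimand.

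**Step 2. Collected scores are discarded too.** SAP 5.4 lets an early termination score fill an analysis visit when it falls inside the window and no scheduled score exists; the Week 4 window is Days 23 to 43. If such a subject's last dose day and early termination visit fall in that window, the score was observed but is set to missing. The analysis is then neither composite nor strictly observed-case.

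**Step 3. Which endpoints carry the rule.** The exception appears in three bullets of 5.5: vIGA-AD success, WI-NRS 4-point reduction, and EASI-50/75/90/100. There is no such statement for vIGA-AD 'clear' or for 'clear or almost clear'.

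**Step 4. Size.** Let p be an arm's composite success rate and d the share of the arm that stops for an AE or lack of efficacy. These subjects are all failures by definition, so removing them leaves the numerator alone and shrinks the denominator:

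observed-case rate = p / (1 - d)

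Inputs: p = 37% active and 22% vehicle, the planning rates in SAP 5.1, used here as if they were composite rates. Values of d are assumptions, since the documents give none. No other data are taken to be missing. The odds ratio is a(1 - v) / [v(1 - a)], with a and v the two observed-case rates.

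| d active | d vehicle | Active | Vehicle | Difference (points) | Shift | Odds ratio |
|---|---|---|---|---|---|---|
| 0% | 0% | 37.0% | 22.0% | 15.0 | 0 | 2.08 |
| 2% | 2% | 37.8% | 22.4% | 15.3 | +0.3 | 2.10 |
| 5% | 5% | 38.9% | 23.2% | 15.8 | +0.8 | 2.12 |
| 5% | 1% | 38.9% | 22.2% | 16.7 | +1.7 | 2.23 |
| 6% | 1% | 39.4% | 22.2% | 17.1 | +2.1 | 2.27 |
| 2% | 5% | 37.8% | 23.2% | 14.6 | -0.4 | 2.01 |
| 1% | 6% | 37.4% | 23.4% | 14.0 | -1.0 | 1.95 |

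For example, 37/0.95 = 38.9 and 22/0.99 = 22.2, difference 16.7; and 37/0.99 = 37.4 and 22/0.94 = 23.4, difference 14.0.

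**Step 5. Direction.** The shift in points is 37·dA/(1 - dA) - 22·dV/(1 - dV). Both arms' rates rise, and in relative terms the arm with more stops rises more. Equal stops still widen the difference, because the active rate is the larger one. The difference narrows only when dV/(1 - dV) exceeds 37/22 = 1.68 times dA/(1 - dA). Either direction is possible.

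**The case against.** The strongest reply is that the rule is deliberate and nothing confirmatory rests on it. SAP 5.5 states both treatments together. The composite estimand is served by the primary analysis and by the mITT, tipping-point and non-responder analyses. The secondary endpoints use multiple imputation as the main analysis, with non-responder imputation alongside, and the exploratory p-values are nominal. This stands and limits the weight of the point. It does not explain why analyses that change the target are labelled sensitivity analyses, or give EASI-50, EASI-90 and EASI-100 an analysis that counts these failures.

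Other replies that stand in part:

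- **PP is partly protected.** SAP 4.3 requires a vIGA-AD assessment in the Week 4 window and at least 80% compliance, so many early stoppers are already out of PP and Moderate PP. The effect there is smaller.
- **Not all of the shift comes from the 5.5 phrase.** A subject who stopped before Day 23 with no Week 4 score would be missing in any plain observed-case analysis. The formula measures the gap from the composite result, not the effect of the phrase alone.
- **Failure here is definitional.** A discarded score could be a clinical success.
- **The gap can largely be diagnosed.** Non-responder results are reported beside the observed-data results, and SAP 7.1 tabulates discontinuation reasons by arm. That helps for the primary and secondary endpoints but does not supply the missing EASI-50/90/100 analysis.
- **Scoring these subjects as failures would nearly repeat the non-responder analysis.** The two would differ only for data missing for other reasons, which is the contrast a sensitivity analysis of this estimand should show.

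A reader might also infer that vIGA-AD 'clear' loses these failures by the same rule. The documents do not support that: 5.5 has no exception for it, so its handling is unstated. The removal of data in SAP 6.2.1 applies only to the source data for multiple imputation.

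**Conclusion.** The point holds and should be corrected before unblinding. The observed-data analyses of vIGA-AD success, WI-NRS response and EASI response on ITT, Moderate ITT and the WI-NRS population, and to a lesser extent those on PP and Moderate PP, do not target the stated estimand. EASI-50, EASI-90 and EASI-100 never count these failures.

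With stops of 1% to 6% per arm and composite success of 37% versus 22%, the difference shifts by roughly -1 to +2 points. That range depends on the assumed rates and on no other missing data; actual rates could put the shift outside it.

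A reader might go further and infer that the primary result or a formally tested secondary result is biased, or that the rule favours the active arm. Neither follows. The primary multiple imputation, mITT, tipping-point and non-responder analyses score these subjects as failures, no confirmatory conclusion depends on the observed-case analyses, and the direction depends on which arm has more such stops.

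**What to change.** In the three bullets of SAP 5.5 (vIGA-AD success, WI-NRS 4-point reduction, EASI-50/75/90/100), replace the two-part parenthetical so that subjects who discontinue for an AE or lack of efficacy are non-responders in the multiple imputation, non-responder imputation and observed-case analyses alike. Only data missing for other reasons stay missing. Deleting the observed-case phrase alone is not enough: the remaining parenthetical names only the other two methods and would leave the observed-case analyses with no rule.

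Add the same sentence for vIGA-AD 'clear' and 'clear or almost clear'. In SAP 12.3, note that scoring these subjects as failures is part of the endpoint definition and so does not conflict with analysing observed data without imputation.

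If the sponsor prefers the current rule, relabel these analyses as supplementary in SAP 12.1.3, 12.2 and 12.5, and state the estimand they target.

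The cost is a few sentences and a small change to the derivation programs, with no new data. Observed-case success rates become slightly lower.
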